Research and Clinical Pharmacology, 2012, 23 (2): 140-143). Additionally, Compound Zhenzhu Tiaozhi capsules can reduce serum TG, TC, and low-density lipoprotein cholesterol (LDL-C) and increase serum HDL-C levels in a hyperlipidemic rat model (Cited from: Tang Chunping, Gong Mengjuan, Guo Jiao, Yang Chaoyan, Chen Fangchao, Yao Hongxia, Chen Yuefeng. The effects of Fufang Zhenzhu Tiaozhi capsules on blood lipid level and hemorheology of rats with hyperlipemia [J]. Journal of Guangdong Pharmacy College, 2010, 26 (6): 612-616).

Based on the above studies, the investigators hypothesize that Compound Zhenzhu Tiaozhi capsules have the potential to effectively improve NAFLD and related biomedical markers. The possible mechanisms include the improvement of SIBO and the function of the intestinal mucosal barrier. The investigators thus designed the following clinical study to test this hypothesis.

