2.3 Secondary Objectives

1. To evaluate the change in intestinal mucosal barrier function by detecting biochemical parameters of the intestinal mucosal barrier; to analyze the relationship between NAFLD and the function of the intestinal mucosal barrier.
2. To explore the trends of small intestinal bacterial overgrowth (SIBO) during the treatment process.
3. To investigate whether lipid profiles and liver biochemical parameters are improved following treatment with Compound Zhenzhu Tiaozhi capsules.
4. To assess whether insulin resistance is improved following treatment with Compound Zhenzhu Tiaozhi capsules.
5. To monitor adverse events and put forward specific solutions for the adverse events.

3. Design, evaluation, and plans

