4.4 Predictors

Univariate and multivariate statistical analyses will be used to analyze therapeutic efficiency.

1. Factors considered for univariate analysis are as follows:

- a. Baseline: life style, gender, age, baseline liver biochemical parameters, baseline fat attenuation index, baseline lipid profiles, baseline quality of life, baseline BMI;
- b. Factors relevant to treatment: dose of medication, insulin resistance, intestinal barrier function, SIBO.

2. Factors considered in multivariate analysis are as follows:

Only factors that have statistical significance in univariate analysis will be entered for multivariate analysis. Additional three factors including insulin resistance, intestinal barrier function, and intestinal bacterial overgrowth will still be considered for multivariate analysis, regardless of univariate analysis results.

5. Definitions

Diabetes: fasting blood glucose ≥ 7.8 mmol/L, or two hours post-75 g glucose drink/or postprandial random glucose ≥ 11.1 mmol/L.

Overweight: BMI > 28 (kg/m²); obese: BMI > 31 (kg/m²); BMI = weight/height² (kg/m²)

Liver biochemical parameters: Detect liver injury and liver excretion function at time of admission and 6 months later.

NAFLD Fibrosis score (NFS): This is a noninvasive method to evaluate liver fibrosis, and is calculated by six variables such as age, BMI, and platelet count. The formula is as follows: $-1.675 + (0.037 \times \text{age}) + (0.094 \times \text{BMI}) + (1.13 \times (\text{hyperglycemia or diabetes; yes} = 1, \text{no} = 0)) + (0.99 \times \text{AST} / \text{ALT}) - (0.013 \times \text{platelet count (x } 10^9 / \text{L)}) - (0.66 \times \text{albumin (g / dL)})$. A score less than -1.455 is used to rule out advanced liver fibrosis.

SIBO: Due to small intestinal stasis, bacteria overgrow in the small intestine, resulting in several clinical symptoms such as malabsorption, diarrhea, anemia, and nutrient absorption disorders. Appropriate use of antibiotic can achieve beneficial effects.

Intestinal barrier function test: detect DAO, D-lac, and LPS, and combine with clinical manifestations to evaluate the function of intestinal mucosal barrier.

SF-36 assessment: SF-36 can comprehensively assess the quality of life from multiple dimensions, and is now widely applied in the evaluation of quality of life, clinical trial results, and clinical efficacy.

6. Definitions of Data Sets

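### SAP 4.4 keeps three markers, most naturally read as post-randomisation values, in its predictor model with no randomised arm, so a marker can look predictive merely because it differs by arm

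*SAP*

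**What the plan says.** SAP 4.4 (Predictors) sets the aim: "Univariate and multivariate statistical analyses will be used to analyze therapeutic efficiency". The model type is not stated.

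Candidate factors come in two lists. The first is "Baseline: life style, gender, age, baseline liver biochemical parameters, baseline fat attenuation index, baseline lipid profiles, baseline quality of life, baseline BMI". The second is "Factors relevant to treatment: dose of medication, insulin resistance, intestinal barrier function, SIBO". Insulin resistance, barrier function and SIBO appear only in the second list, next to dose, with no baseline label and no visit. Randomised arm is in neither list.

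The general entry rule is "Only factors that have statistical significance in univariate analysis will be entered for multivariate analysis". The three markers are exempt, whatever their univariate result: "Additional three factors including insulin resistance, intestinal barrier function, and intestinal bacterial overgrowth will still be considered for multivariate analysis".

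Other sections show what these markers are in this trial:

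- SAP 2.3 makes insulin resistance an on-treatment question ("To assess whether insulin resistance is improved following treatment with Compound Zhenzhu Tiaozhi capsules") and asks about change in barrier function and the course of SIBO during treatment.
- SAP 4.2 lists breath testing and the barrier markers as secondary efficacy parameters.
- Protocol 4.4 (therapeutic effects) assesses insulin resistance at 1, 3 and 6 months.
- SAP 9.3, item 3, presupposes that all three are measured at intermediate visits.
- Protocol I (Background) says of the capsule: "The possible mechanisms include the improvement of SIBO and the function of the intestinal mucosal barrier". That sentence covers SIBO and barrier function, not insulin resistance.

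On the other side, SAP 9.5 includes SIBO and insulin resistance, but not barrier function, among screening and baseline indicators.

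**The concern.** A factor measured after randomisation can be changed by treatment. If it enters a model of response and arm does not, it carries information about which arm the patient was in. The planned response rates differ widely between arms, so any marker that also differs between arms will be associated with response in the pooled data, even if it says nothing about response among patients on the same treatment. Reported as an independent predictor, such a marker would seem to support the gut-liver mechanism, which SAP 2.2 (item 4) makes a primary objective.

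A second problem would follow if the analyst added arm to the model while keeping on-treatment markers. Where a marker lies on the path from drug to response, conditioning on it removes part of the arm effect from that model.

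The section leaves both the visit and the arm term open, in an open-label trial whose SAP section 7 provides for real-time analysis of the data.

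**Working it through.** The plan gives no figure on this point to reproduce. It supplies response rates and numbers; the marker effects must be assumed.

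**Inputs from SAP 3.4.** Response 69% (capsule), 44% and 44% (metformin, simvastatin), 10% (TLC); two-sided alpha 0.05; 49 per arm with 10% loss, so 49 × 0.9 = 44.1, or 44 evaluable per arm and 176 in total.

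**Assumptions.** A marker has SD 1 within each arm and no link to response within any arm. The capsule shifts it by s against TLC and each drug by s/2, with s from 0.4 to 1.0 SD.

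**Arm omitted: closed-form check.**

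- Mean response = (0.69 + 0.44 + 0.44 + 0.10)/4 = 0.4175. Variance = 0.4175 × 0.5825 = 0.2432.
- The mean marker value over arms is s/2, so the arm deviations are s/2, 0, 0 and −s/2.
- Covariance of marker and response, wholly between arms = [0.2725 × s/2 + 0.3175 × s/2]/4 = 0.07375 s.
- Marker variance = 1 + [2 × (s/2)²]/4 = 1 + s²/8.
- Correlation r = 0.07375 s / √[(1 + s²/8) × 0.2432]; expected test statistic z ≈ r√176; chance of significance ≈ Φ(z − 1.96) + Φ(−z − 1.96).

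| s (capsule) | drugs | r | z | chance significant |
|---|---|---|---|---|
| 0 | 0 | 0 | 0 | 5% |
| 0.4 | 0.2 | 0.059 | 0.79 | 12% |
| 0.6 | 0.3 | 0.088 | 1.16 | 21% |
| 0.8 | 0.4 | 0.115 | 1.53 | 33% |
| 1.0 | 0.5 | 0.141 | 1.87 | 46% |

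Logistic simulation on the same assumptions agrees: about 12% to 47% at 44 per arm, and about 5% when arm is in the model or the marker does not shift.

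**Three independent null markers together, arm omitted (simulation, 44 per arm).** With shifts of 0.5/0.25 SD each marker is significant in 15% of trials and at least one in 40%. With 1.0/0.5 SD the figures are 34% and 75%. With no shift, as for admission values, they are 5% and about 14%. The per-marker rate is lower than for a single marker because the three share the same between-arm signal.

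**Arm added, on-treatment markers kept (simulation, 44 per arm, capsule v metformin).** The crude odds ratio is (0.69/0.31)/(0.44/0.56) = 2.83; simulated medians are 2.8 to 2.9, with power about 0.64 to 0.66. For shifts of 1.0/0.5 SD:

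| assumed share of crude log odds ratio carried by the markers | adjusted odds ratio | power |
|---|---|---|
| 0% | 2.95 | 0.62 |
| 25% | 2.25 | 0.40 |
| 50% | 1.87 | 0.25 |
| 75% | 1.55 | 0.14 |
| 100% | 1.38 | 0.09 |

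With shifts of 0.5/0.25 SD and shares of 25% to 100%, the odds ratio lies between 2.3 and 2.5 and power between 0.46 and 0.30. The share is a nominal label: odds ratios are not collapsible, so the adjusted value does not reach 1 at 100%. The gap between crude power here and the 0.80 in SAP 3.4 is a separate matter.

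**The case against.** The strongest reply is that the section never says the markers are on-treatment values. It gives no visit, and SAP 9.5 lists SIBO and insulin resistance at baseline. If admission values are meant, neither problem arises. This stands as a limit on certainty, but it does not remove the point. SAP 4.4 attaches the word baseline to most of its first list, leaves it off these three markers and groups them with dose. SAP 9.5 does not say its values feed SAP 4.4, and it omits barrier function.

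Second, a reader might infer that the plan adjusts away the capsule's effect. The documents do not support that. SAP 4.4 is headed as a search for predictors, lists no arm term and is not called the treatment comparison. Protocol 4.4 compares the capsule with the other three groups at matching visits and attaches no covariates. Attenuation would arise only if arm were added and the markers mediate the effect.

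Third, a reader might infer that one harm or the other must occur. That is also too strong. With arm in the model and markers that do not mediate, the odds ratio stays at about 2.95 and each marker keeps its 5% error rate. A marker may also genuinely predict response within arms.

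Fourth, dose is among the candidates. Because it differs by treatment, it could partly encode arm and reduce the 12% to 47%. This stands, but dose must first pass the univariate screen, and the plan does not say how doses of different drugs would be put on one scale.

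Fifth, the text says the markers will be considered, which is weaker than forced entry. Even so, they bypass a screen that every other factor must pass.

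Finally, Protocol 4.5 already relates change in barrier function and SIBO to change in liver and metabolic measures within the capsule group. That analysis is free of the between-arm artefact, so the mechanism question does not rest on SAP 4.4 alone.

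**Conclusion.** The point holds in a limited form. As written, SAP 4.4 most naturally puts post-randomisation markers into a model of response without randomised arm. A marker with no link to response within arms would then be declared an independent predictor in about 12% to 47% of trials at 44 per arm, instead of 5%. The range rests on assumed capsule shifts of 0.4 to 1.0 SD with half that for the two drugs, the plan's own response rates, and no encoding of arm through dose. The documents give no marker effects, so the range illustrates the risk and does not predict it.

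Attenuation of the arm effect is a conditional, secondary risk confined to this model. Nothing here touches the primary between-group comparison. Since this is a predictor analysis, the matter should be fixed but is not critical.

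**What to change.** In SAP 4.4:

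1. Move the three markers to the baseline list and state that their admission values are used. The admission tests in the Protocol's Prescriptions section (4.2, Biochemical assessments) include fasting insulin, fasting glucose, barrier function and the breath test.
2. Include randomised arm in the multivariate model, whatever the univariate result.
3. Keep post-randomisation marker values out of any model used to estimate the treatment effect or to name predictors.
4. Analyse on-treatment change separately, through the change-against-change analysis in Protocol 4.5 or a mediation analysis labelled exploratory.

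The cost is a change of SAP wording, a few more model terms (three for a four-level arm factor) and some analysis work. No new data are needed.

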6.1 Full Analysis Set (FAS)

The FAS refers to the combination of qualified cases and shedding cases, but without exclusion cases. Baseline and demographic characteristics will be analyzed. Intention to treat (ITT) analysis will be used in the absence of primary outcome measures.

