2.4. The following individuals will be considered as lost to follow-up: first, patients who suddenly present serious physical or mental diseases (not related to the study) during the study period, such as malignant tumors, severe mental illness, traffic accidents, etc.; second, patients who have serious side effects in which the symptoms can be relieved by discontinuing the study medication; third, patients who actively ask to stop using the study medication or refuse to come to follow up visits. Fourth,

patients who need to take other medications due to the development of other new diseases, where the new medications may interfere with the study results, such as hypoglycemic agents, including insulin.

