6.2 Per Protocol Set (PPS)

The PPS refers to the set of subjects who meet the inclusion criteria and complete the research project, which also means they comply with the research protocol, have good compliance, do not use banned substances during trial, and have completed the case report form (CRF). The PPS analysis is mainly used to assess primary efficacy.

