6.3 Safety Set (SS)

SS analysis will be performed for all randomized subjects who received at least one dose of the study drugs and have at least one safety assessment. The missing value of safety cannot be carried forward. Some excluded cases can be evaluated, such as a case whose age exceeds the inclusion criteria, but will not include cases who use prohibited drugs. The rate of adverse events will be calculated using the total cases in the SS as the denominator.

7. Interim Analysis

Some specialized staff in the Department of Statistics will be responsible for the real-time statistical analysis of the study data and will present the results with an analysis report.

8. Data Verification

The final data analysis should not be started until all data have been verified, questions have been resolved, and the databases have been locked. We aim to demonstrate that the source of the data is real and valid, and will ensure that the database is locked prior to data analysis.

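### The FAS removes undefined exclusion cases, which appear to include on-treatment users of prohibited drugs, so no efficacy set keeps all randomised patients

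*SAP*

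**What the plan says.** **SAP 6.1 (FAS).** "The FAS refers to the combination of qualified cases and shedding cases, but without exclusion cases". Qualified, shedding and exclusion cases are not defined in either document. The section names baseline and demographic characteristics as what will be analysed, then adds: "Intention to treat (ITT) analysis will be used in the absence of primary outcome measures".

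**SAP 6.2 (PPS).** Members must meet the entry criteria, complete the study, comply, and, among other conditions, "do not use banned substances during trial". The section ends: "The PPS analysis is mainly used to assess primary efficacy".

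**SAP 6.3 (Safety Set).** The set is "all randomized subjects who received at least one dose of the study drugs and have at least one safety assessment". A later sentence qualifies this: "Some excluded cases can be evaluated, such as a case whose age exceeds the inclusion criteria, but will not include cases who use prohibited drugs". No list of prohibited drugs is given.

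**Protocol 2.4 (under Enrollment).** "The following individuals will be considered as lost to follow-up", followed by four groups. The fourth is patients who need other medicines for a new disease, "where the new medications may interfere with the study results, such as hypoglycemic agents, including insulin".

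**SAP 9.3 (missing values).** A missing primary outcome is carried forward in four situations. The withdrawal rules cover patients without a response and patients who leave because of full recovery.

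**The concern.** The PPS already leaves out anyone who used a banned substance, failed to comply or did not complete. The FAS is the only other efficacy set, so it is the only place where the randomised comparison could be kept whole. If the FAS also loses patients because of a drug they took after randomisation, agreement between the two sets would not be reassuring, since both would have lost the same patients. Moving the primary analysis from the PPS to the FAS would not cure this.

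The trial is open-label (SAP 3.1). Whether a patient is given another drug, and whether that patient is then filed as an exclusion or as a dropout, can depend on the arm and on how the patient is doing. With the terms undefined, the filing could be settled after both are known.

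**Working it through.** **1. The plan's own attrition figure.** SAP 3.4 starts from 44 per group and allows 10% loss: 44 / (1 − 0.10) = 48.9, rounded up to 49; 49 × 4 = 196. This reproduces. The allowance is 49 − 44 = 5 patients per group, or 5/49 = 10.2%.

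**2. Who is an exclusion case?** The text supports the reading in three steps.

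- SAP 6.3 is the only section that illustrates an excluded case. It sets over-age patients, who may return to the Safety Set, against users of prohibited drugs, who may not. Naturally read, both are kinds of excluded case.
- The population in 6.3 is randomised and dosed, so the exclusion is applied after randomisation.
- SAP 6.2 places banned-substance use during the trial, so at least some of it is an on-treatment event.

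Together these indicate that SAP 6.1 drops randomised patients for something that happened on treatment. Even if exclusion cases were only over-age patients, the FAS would still omit some randomised patients.

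**3. SAP against Protocol 2.4.** Take a patient who starts insulin for a new disease at month 3.

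| Route | Status | In the FAS? |
|---|---|---|
| Protocol 2.4, if lost to follow-up means shedding | dropout | yes |
| SAP 6.3, if insulin counts as prohibited | excluded case | no |

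Neither condition is written down, and no section says which route applies.

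**4. Possible size.** The planned rates are 69% (capsules) and 44% (metformin, simvastatin), from SAP 3.4. The documents give no rate of prohibited-drug use. I assume that k of 49 patients are removed from an arm, that all k would count as Invalid if kept, and that the FAS shows the planned rates in those who remain.

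All-randomised rate = FAS rate × (49 − k) / 49.

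- k = 5, capsule arm only: 0.69 × 44/49 = 62.0%; 62.0 − 44.0 = **18.0 points**.
- k = 5, comparator only: 0.44 × 44/49 = 39.5%; 69.0 − 39.5 = **29.5 points**.
- k = 5, both arms: 62.0 − 39.5 = 22.4 points (from unrounded rates, 25 × 44/49).
- k = 2, capsule arm only: 0.69 × 47/49 = 66.2%; difference 22.2 points.
- k = 2, comparator only: 0.44 × 47/49 = 42.2%; difference 26.8 points.
- k = 0: 25 points.

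In each case the FAS would show 25 points. If the removed patients responded at the same rate as the others in their arm, the all-randomised difference would also stay at 25. The distortion comes from removal that is related to outcome.

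**The case against.** The case against rests on how much is inferred, and most of it stands as a limit on the claim.

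- SAP 6.3 defines the Safety Set. It does not say that its excluded cases are the exclusion cases of 6.1, nor when the drug was taken. SAP 6.2 can also be read the other way: making banned-substance use a condition of the PPS is consistent with such patients leaving the PPS but staying in the FAS. This is not decisive, because the PPS definition repeats the inclusion criteria as well.
- A reader might infer that the SAP flatly contradicts Protocol 2.4. It does not. The Protocol defines no FAS, and a contradiction needs two unstated equations: lost to follow-up with shedding, and interfering medicines with prohibited drugs. The sections are unreconciled, which is a weaker statement.
- A reader might infer that the FAS is labelled the ITT population. The ITT sentence in 6.1 is tied to absent primary outcomes and sits more naturally with the carry-forward rules of SAP 9.3. What ITT means there is unclear.
- Primary efficacy is assigned mainly to the PPS, and no section clearly specifies a FAS comparison of the primary endpoint. Rewording the FAS would not by itself move the main result.

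What survives is that no text places these patients in the FAS, the most natural reading removes them, and the alternative reading needs the same wording to make it certain.

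**Conclusion.** The point holds in a limited form. SAP 6.1 removes an undefined group of randomised patients, and SAP 6.3 with SAP 6.2 indicates that the group includes on-treatment users of prohibited drugs. On that reading no efficacy set keeps all randomised patients, and the FAS cannot serve as an intention-to-treat check on the PPS. The status of these patients is also unreconciled with Protocol 2.4.

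Under the assumptions above, with up to 5 of 49 removed from one arm, an apparent 25 points corresponds to between 18.0 and 29.5 points in all randomised patients. The number removed and their outcomes are assumed. All being non-responders is a deliberately unfavourable choice, and the true effect may be small.

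It is tempting to conclude that the wording favours the capsules, for instance because metformin patients already take a hypoglycaemic agent. The documents do not support a direction: nothing in them says which arm would start more interfering drugs, and bias against the capsules is equally possible.

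SAP 6.3 has a related internal inconsistency. It takes every randomised, dosed patient with a safety assessment and then drops users of prohibited drugs, so their adverse events leave the reported rates. This should be corrected before the database is locked.

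**What to change.** - **SAP 6.1:** define the FAS as all randomised patients analysed in their assigned arm, and state that prohibited or interfering drug use after randomisation never removes a patient from it. If any exclusion is kept, call the set a modified FAS and limit exclusions to entry-criteria failures shown by information dated before randomisation and assessed without knowledge of arm.
- **SAP 6.3:** delete the removal of prohibited-drug users from the Safety Set.
- **SAP 6.1, 6.3 and Protocol 2.4:** define qualified, shedding and exclusion cases, identify the drugs the SAP calls prohibited, and give each patient who starts such a drug one status in both documents.
- **Reporting:** present the primary endpoint on this FAS beside the PPS.

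The cost is wording in the SAP and in Protocol 2.4, and a missing-outcome rule: SAP 9.3 has no withdrawal rule for a patient who had responded, but not fully recovered, before leaving. Keeping these patients may slightly dilute the estimated difference. No additional patients are needed.
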